The clinical presentation of scabies has been previously described in other tropical regions. A recent study conducted in Yaoundé showed lesions were most commonly present in the infragluteal folds, on the wrists and in the intergluteal folds. Types of lesions were also documented, with crusty lesions being the most common type(8).

For persons never before affected by scabies it can take up to 6 weeks for symptoms to begin, while the mites can already be spread during this asymptomatic period. However in reinfestation symptoms usually occur much earlier(1-4 days)(9).

There exist different agents for the treatment of Scabies with comparable efficacy(10–12). Ivermectin seems to be most effective for large populations with high prevalence of scabies(10). However the use of ivermectin can lead to serious adverse events in patients with high concentration of *Loa Loa* microfilariae in the blood(13). Since *Loa Loa* is endemic in Gabon(14), treatment with ivermectin for Scabies should only be given if high *Loa* parasitemia can be excluded. Furthermore, only limited safety data exists for children under 5 years of age or weighing less than 15 kg, a group in which scabies is common(9).

Permethrin is the first line topical treatment for Scabies, however it comes at a higher cost per treatment, and is more difficult to obtain in Gabon than Benzyl Benzoate, a substance which also offers good efficacy and safety(10–12).

It is recommended that the contact persons of an affected individual shall also be treated at the same time, to ensure long term success of treatment, prevent reinfestation and infestation of contact persons(9,10,15). However this recommendation lacks a solid background of evidence. A recent review concluded that the effects of treating contact persons to prevent new infestation are unknown(16).

There is currently an outbreak of itching lesions suggestive of scabies in Gabon that the local population has named “gratti gratta” but there has been so far no raised attention from the local medical scientific community to describe these lesions and definitely attribute the diagnosis of scabies and sensitize the population in measure for the control of the epidemic.

Research question

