We propose a randomized controlled trial comparing treatment of only affected persons presenting at our medical research center (which we will call individual treatment) to treatment of the entire household (which we will call household treatment), with both groups using the same treatment regimen with benzyl benzoate. We hereby aim to assess the practice of systematically recommending household treatment and if it provides a benefit for the index case by preventing reinfestation.

We will also assess the number of household members affected 4 weeks after treatment, by examining all household members that are present on the day of the visit. Since the presence of itching and skin lesions in a household with a diagnosed scabies case is known to be highly specific (15,17), we will also assess the number of probable scabies cases per household before and after treatment according to the judgment of the household responsible person. Cases identified this way will be defined as “probable” and cases identified through clinical diagnosis by a physician will be defined as “confirmed”.

We will further assess clinical characteristics of Scabies and demographic factors associated with its appearance in Lambaréné, Gabon, and surroundings. Although similar studies have been conducted elsewhere, little is known about Scabies in Gabon. A better understanding of the demographic profile of persons affected by the disease can benefit future control of the disease.

Study Objectives (Aims)

Primary objectives

To compare the effectiveness of individual vs household treatment for persons affected by scabies.

Secondary objectives

To compare the effectiveness of individual vs household treatment in terms of proportion of household members affected after 4 weeks.

To describe the clinical presentation of scabies and demographic profiles of persons affected presenting at our medical research center in Lambaréné, Gabon.

To assess the tolerability and safety of benzyl benzoate.

Endpoints

Primary Endpoint

The primary efficacy outcome will be clinical cure after 4 weeks.

Secondary Endpoint

Secondary endpoints will include the rate of probable and confirmed scabies cases per household after 4 weeks.

Methods and Materials

Study Population

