Study treatment and follow up

For the treatment part of this study index cases will be randomized in either of two groups and subjects of the respective household will follow the randomization outcome of the index case. Randomization will be done in RedCAP. In the first group only subjects affected by scabies shall be treated. In the second group all persons living in the same household as the index case shall be treated, and treatment will be dispensed according to the number of household members stated by the household responsible person. For both groups the choice of treatment will be a single application of benzyl benzoate 25%, which shall be mixed with an equal quantity of water for older children and with 3 parts of water for infants. Subjects will be instructed on the use of the treatment and given a standardized leaflet with instructions, however the use of the treatment will not be supervised, making this an intervention conducted in a real world setting.

Subjects will be followed up after 4 weeks. At follow up visits the subjects will be questioned about the symptoms of scabies and any adverse events experienced and examined by a physician. Cure will be defined as the clinical improvement in lesions with no new lesions. All household members present at this visit will also be examined for scabies. Subjects and household members considered not cured or newly infested will be treated.

Safety

Benzyl Benzoate is generally safe to use for all persons, including infants and pregnant women. It is contraindicated only for persons with known hypersensitivity to benzyl benzoate, which will constitute an exclusion criterium. Adverse events include skin irritation and stinging sensation(21). In case of accidental ingestion subjects are requested to contact the principal investigator.

Ethical Considerations

To maintain randomization into the individual and household treatment groups and to avoid preferential withdrawal, loss to follow up, or spillover effects the informed consent process will be performed in a two step approach.

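### The cure definition does not say how reinfestation or repeat scabicide use before week 4 is recorded or counted, so a reinfested and retreated subject can be scored as cured

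*Combined protocol and SAP*

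**What the plan says.** The Research question section gives the purpose of the trial: to assess household treatment and "if it provides a benefit for the index case by preventing reinfestation". Under Primary Endpoint, "The primary efficacy outcome will be clinical cure after 4 weeks".

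The operational rule is under Study treatment and follow up:

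- **Schedule:** "Subjects will be followed up after 4 weeks". No other contact is described.
- **Data:** "At follow up visits the subjects will be questioned about the symptoms of scabies and any adverse events experienced and examined by a physician". Use of further scabicide is not listed.
- **Rule:** "Cure will be defined as the clinical improvement in lesions with no new lesions". The period over which a lesion counts as new is not stated.
- **Retreatment:** both arms receive one unsupervised application. Treatment of subjects who are not cured or newly infested is mentioned only together with the follow-up visit. Earlier treatment is not prohibited, recorded or given a place in the endpoint.

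The introductory text before the Research question section says of symptom onset: "However in reinfestation symptoms usually occur much earlier(1-4 days)(9" (the 9 is a reference number).

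**The concern.** Reinfestation happens at some time between the study application and week 4, but the endpoint is assessed once, at the end of that interval. By the protocol's own account, symptoms of reinfestation appear within days. A subject reinfested in the first or second week could thus have symptoms for two weeks or more before anyone from the trial looks. If that subject obtains treatment in the meantime, the skin at week 4 may be improved with nothing new to see, and the subject can be scored as cured.

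Retreatment of this kind follows failure. The protocol expects more failures in the individual arm, so more failures would be converted to cures there. A null result could then not be told apart from reinfestation that occurred and was treated. No analysis could repair this afterwards, because the information needed is not among the data listed for collection.

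**Working it through.** **Inputs**

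- From Sample size: cure 70% (individual) and 95% (household), 35 affected subjects per group, 80% power, alpha 0.05. Sidedness is not stated; two-sided is assumed.
- Not in the documents: the share *f* of failures that are retreated before week 4 and then scored cured. It is assumed, with a range from 10% to one third.
- The planning rates are taken as the rates before any such conversion, and subjects as independent, as in the protocol's own calculation.

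**Step 1. Reproduce the plan's figure.** Two proportions, pooled variance under the null, mean rate (0.70 + 0.95)/2 = 0.825:

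n = [1.960 × √(2 × 0.825 × 0.175) + 0.842 × √(0.70 × 0.30 + 0.95 × 0.05)]² / 0.25²

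= [1.960 × 0.5374 + 0.842 × 0.5074]² / 0.0625 = 35.06.

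The stated 35 per group is reproduced. Power at n = 35 is 79.9%.

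**Step 2. Apply the conversion.** With the same *f* in both arms:

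- individual arm: 0.70 + 0.30 *f*
- household arm: 0.95 + 0.05 *f*
- difference: 0.25 × (1 − *f*)

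Expected failures converted per 35 subjects are 10.5 *f* (individual) and 1.75 *f* (household), a ratio of 6 to 1.

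**Step 3. Power.** Power = Φ{[d − 1.960 × √(2p̄(1 − p̄)/35)] / √[(p₁(1 − p₁) + p₂(1 − p₂))/35]}, where d = p₂ − p₁ and p̄ is the mean of the two rates.

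| *f* (assumed) | Individual | Household | Difference (points) | Converted, individual / household | Power |
|---|---|---|---|---|---|
| 0 | 70.0% | 95.0% | 25.0 | 0 / 0 | 79.9% |
| 10% | 73.0% | 95.5% | 22.5 | 1.05 / 0.18 | 74.4% |
| 20% | 76.0% | 96.0% | 20.0 | 2.1 / 0.35 | 68.1% |
| 1/3 | 80.0% | 96.7% | 16.7 | 3.5 / 0.58 | 58.7% |

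For *f* = 10%: p̄ = 0.8425, the two standard errors are 0.0871 and 0.0828, and (0.225 − 1.960 × 0.0871)/0.0828 ≈ 0.656, so power is 74.4%.

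**Step 4. A variant.** If conversion applies only to the 25-point excess of failures in the individual arm, with the household arm fixed at 95%, power is 73.3% at 10%, 65.5% at 20% and 56.8% at 30%.

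**Step 5. Direction.** The bias is towards no difference when 0.30 × f(individual) exceeds 0.05 × f(household). It reverses only if the household-arm share is more than six times the individual-arm share.

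**The case against.** A reader might infer that every subject reinfested and retreated before week 4 counts as cured, or that cure depends on the state of the skin on that day alone. The documents do not support this. Improvement and new lesions both describe change from an earlier state. Under Scabies Diagnosis and Data Collection, lesions are described by location and spread, severity is graded by lesion count, and characteristic lesions are photographed. Subjects are also asked about symptoms at week 4. If *no new lesions* means none since treatment, a subject who reports lesions that came and went is not cured. That reading is open, but so is the other, and the definition does not require recall of resolved lesions. What stands is ambiguity, not a certain misclassification.

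Other objections also have force:

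- **Frequency.** The protocol plans no retreatment before week 4, so the problem arises only from treatment outside the plan, and no rate is given. The introductory text says only that permethrin is harder to obtain in Gabon than benzyl benzoate, which does not show how many subjects would seek more. The upper end of the range is demanding: if retreatment succeeds at the 70% planning rate, *f* = 20% needs 0.20/0.70 = 29% of failures to be retreated, and *f* = 1/3 needs 48%. Reinfestations that are not retreated remain detectable at the visit.
- **Choice of endpoint.** The primary objective is effectiveness and the setting is described as real-world. Status at 4 weeks regardless of extra treatment is a legitimate pragmatic endpoint, so a composite is not the only defensible definition. The stated interest in reinfestation is the reason to count retreatment.
- **Arm-dependent supply.** Household-arm homes receive treatment for all stated members, use is unsupervised, and no blinding is described. Repeat use for lingering itch may therefore differ by arm, and scoring every extra application as failure could misclassify unevenly. For this reason the fix ties failure to retreatment for new or persistent lesions and reports the alternatives alongside.

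**Conclusion.** The point holds in a limited form. The protocol neither fixes the reference period for new lesions nor provides for recording or counting scabicide use between the study application and week 4. A reinfested and retreated subject can be scored as cured. With equal conversion in both arms and the protocol's own planning rates, the bias is towards no difference, and the listed data would not show it.

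The size is unknown. Over the assumed range of 10% to one third, the difference shrinks from 25 points to between 22.5 and 16.7. These figures are illustrations and not a forecast: the share has no basis in the documents, and household clustering is left aside. Because the calculation gives almost exactly 80% power, there is no slack to absorb even one or two converted failures in the individual arm. The change is worth making because it is cheap and the information cannot be recovered later.

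**What to change.** 1. Add to the existing week-4 interview a question on any scabies treatment since the study application, with date, reason and source. Log unscheduled returns to the centre for scabies.
2. State in the cure definition that no new lesions means none since the study application, whether reported by the subject or seen by the physician.
3. Pre-specify that a subject retreated for new or persistent lesions before week 4 counts as not cured in the primary analysis.
4. Report by arm two sensitivity analyses: cure regardless of retreatment, and cure with any retreatment counted as failure.

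If the planning rates describe outcomes before retreatment and interim retreatment is fully reported, this keeps the planned 70% versus 95% contrast and about 80% power under the protocol's own formula.

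The cost is a short addition to the endpoint definition, a few REDCap fields at a visit that already takes place, and a simple log. The downside is that retreatment is self-reported, some of it will be for lingering itch, and it may differ by arm because household-arm homes hold more product. The paired analyses show how much this matters. The change affects only what is recorded and how the outcome is counted, not who may be treated.
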